## 9.6 Quality Control

The study will be carried out according to Exponent's Quality Management System (QMS), with specific procedures being consistent with the International Society for Pharmacoeconomics's Guidelines for Good Pharmacoeconomics Practices (<http://www.pharmacoepi.org>), as well as the FDA Best Practice Guidance document (<http://www.fda.gov/Drugs/GuidanceComplianceRegulatoryInformation/Guidances/>). In particular, the QMS at Exponent ensures that processes and deliverables are documented, reviewed, and validated in sufficient detail to allow for subsequent re-examination or replication. Exponent's quality management system is independently assessed against the most recognized and comprehensive international standard for quality management systems, ISO 9001. Exponent complies with the ISO 9001:2015 standard; the ISO 17025:2017 standard; U.S. Code of Federal Regulations, Title 10, Part 50, Appendix B; U.S. Code of Federal Regulations, Title 10, Part 21; and the respective advertising policy for each registration, accreditation, and approval.

The core project team will consist of at least one Principal Scientist who will provide scientific oversight of the study, a senior epidemiologist who will manage day-to-day aspects of the scientific conduct of the study, research analyst(s), and a project manager. Project management is integrated into the project team and supports the development of the project plan, monitoring timelines and budgets, securing appropriate study resources, and facilitating completion of contracted deliverables. In addition, Exponent staff members will support the project team by providing review and quality assurance of documents and programs associated with the conduct of the study, including assurance of appropriate data confidentiality, storage, and management.

## 10 LIMITATIONS OF THE DATA AND RESEARCH METHODS

### 10.1 Electronic Health Data

All EHR databases and healthcare registries have certain inherent limitations because the data are collected for clinical patient management, administration, and other non-research purposes. EHR data represent the intent of the prescriber through the written prescription for a medication; they do not indicate that a medication was filled, consumed, or taken as prescribed.

The EHR data will not include healthcare encounters or prescriptions from providers that do not contribute to the EHR aggregating entity (Arcadia). This can result in under-capture of some medication exposure. In addition, patients prescribed medications may not have them dispensed and may not consume them as prescribed even when they are dispensed. This can overestimate some patients' actual medication exposure.

### 10.2 Unmeasured Patient Risk Factors

In this study, robust PS adjustment relies on accurate measurement of risk factors for MACE. As such, the lack of important risk factors can introduce unmeasured confounding, where these risk factors remain imbalanced between groups after PS adjustment. The use of an active comparator will mitigate some unmeasured confounding, because it shares the same indication as NB. Self-controlled designs are not subject to measured or unmeasured confounding by factors that do not vary over the observation window. Therefore, the case-crossover study will help inform the extent to which residual confounding may affect the cohort analysis.

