## 5 RESEARCH QUESTIONS AND OBJECTIVES

The study will assess whether patients who initiate treatment with NB are at an elevated risk of MACE compared with patients who initiated treatment with lorcaserin, an active comparator chosen to reduce potential confounding. Lorcaserin was approved in the U.S. under the brand names BELVIQ® and BELVIQ XR® for the same indication as NB, and withdrawn from the market due to cancer safety concerns in 2020. Lorcaserin is not believed to have adverse effects on cardiovascular outcomes. The CAMELLIA-TIMI 61 trial was a comparison of lorcaserin relative to placebo in overweight and obese patients with cardiovascular disease and cardiovascular disease risk factors. The trial found no difference in the rate of cardiovascular events.

The study's main objective is to compare the incidence of the primary endpoint (MACE) between initiators of NB and initiators of lorcaserin (1.0). The study will also compare the incidence of the secondary endpoint, consisting of each *component* of MACE, between initiators of NB and initiators of lorcaserin, across the following subgroups (1.1):

- Patients with obesity (i.e., most recent BMI measurement  $\geq 30$  kg/m^2);
- Patients with a diagnosis of hypertension, regardless of BMI;
- Patients with a diagnosis of type 2 diabetes mellitus, regardless of BMI;
- Patients with a diagnosis of dyslipidemia, regardless of BMI.

The study's additional objectives aimed at testing the robustness of the methods are:

- To assess the comparability of findings from an EHR study to those of a 2018 clinical trial, aligning with the RCT DUPLICATE Initiative (2.0);
- To quantify differences in cardiovascular safety endpoints between the clinical trial and the results of this EHR study (2.1);
- To conduct other sensitivity analyses, including a self-controlled, case-crossover analysis to quantify the potential effect of NB on MACE (2.2).

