**Figure 1. NB safety study design**

[figure not shown]

For the cohort, among the subset of patients with EHR data whose records can be linked to health insurance claims, we will assess the concordance between receiving a prescription for NB and lorcaserin (in the EHR) and filling the prescription (in the claims).

The time of entry into the NB cohort will be the date of first prescription for those taking CONTRAVE®, the date of the second overlapping prescription of naltrexone or bupropion in the case of concomitant use of naltrexone and bupropion, or the date of first prescription for lorcaserin from date of approval in the U.S. to withdrawal from the market, as applicable.

In the case-crossover study, a 90-day hazard window will immediately precede the index event date within which the occurrence of a prescription or dispensing will define exposure status. Similarly, a 90-day referent window will precede the hazard window, with exposure status designated comparably. A 30-day washout window between the hazard and referent windows will be used to mitigate any carryover effects from the prior exposure. Please see **Figure 2** for a visual depiction of the case-crossover study design.

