### 9.5.3 Statistical Model for Cohort Analysis

For all primary study objectives, weighted Poisson models will be used to estimate IRDs and IRRs (and 95% CIs), adjusted for all covariates included in the PS model. Robust variance estimators will be used to account for the weighting. Analyses will be conducted amongst the overall NB cohort and also stratified by initiators of CONTRAVE® and those with overlapping, concomitant use of Naltrexone and Bupropion.

For the secondary objective of assessing the comparability of findings in a RWD cohort with the lorcaserin clinical trial, we will conduct a time-to event analysis in the propensity-score matched cohort. We will produce hazard ratios (HR) and 95% confidence intervals using a weighted Cox proportional-hazards model with the stratification factor as a covariate.

Additionally, informed by previous work in the RCT DUPLICATE Initiative, we will examine the following metrics in concert to assess the comparability in findings between the CAMELLIA-TIMI 61 trial and findings in the data:

- Regulatory agreement, which is the ability of the study using RWD to replicate the direction and magnitude of the RCT;

- Estimate agreement, defined as a HR from the replication study that was within the 95% CI for the RCT estimate;
- Standardized difference between the RCT and replication effect estimate, with a p-value < 0.05 considered statistically significant.

Conditional logistic regression models will be used to compare the odds of exposure to NB in the hazard window to the odds of exposure in the referent window (i.e., odds ratio) for the case cross-over design.

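### The case-crossover has no term for changes in healthcare contact before MACE, so its odds ratio can move off 1 in either direction with no drug effect; a contact-adjusted model and a descriptive lorcaserin run would show this cheaply.

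*Combined protocol and SAP*

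**What the plan says.** Section 10.2 gives the case-crossover an interpretive role: "the case-crossover study will help inform the extent to which residual confounding may affect the cohort analysis". The reason offered is that "Self-controlled designs are not subject to measured or unmeasured confounding by factors that do not vary over the observation window".

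Section 6.5.1 sets the windows. On the hazard side, "a 90-day hazard window will immediately precede the index event date within which the occurrence of a prescription or dispensing will define exposure status". On the comparison side, "a 90-day referent window will precede the hazard window, with exposure status designated comparably". Thirty days separate the two, so the referent window covers roughly days 120 to 210 before the event. Section 6.3 admits only MACE cases with an earlier NB record.

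For the analysis, section 9.5.3 says: "Conditional logistic regression models will be used to compare the odds of exposure to NB in the hazard window", against the referent window. It names no covariate, control series or negative control. Healthcare utilization appears in section 9.4, but only as an input to propensity scores.

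On the comparator, section 5 says: "Lorcaserin is not believed to have adverse effects on cardiovascular outcomes".

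**The concern.** The exposure variable is a record, not drug on hand. Section 10.1 notes that the EHR shows what the prescriber wrote, and a written order usually needs some contact with the patient. If contacts become more frequent as MACE approaches, the hazard window offers more chances for an NB order than the referent window does. The same person then looks more exposed just before the event although the drug does nothing.

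Matching within person does not remove this, because contact frequency differs between a person's own windows. A trend series from non-cases would not remove it either, because the change is specific to people nearing an event.

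The reverse is also possible. If NB prescribing falls before the event, for instance as a patient's condition worsens, the odds ratio drops below 1.

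What is at stake is the reading of the result. An odds ratio away from 1 could be taken as a drug signal, or as evidence about confounding in the cohort, when it reflects care before the event. The report is intended for FDA (section 13).

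**Working it through.** The plan gives no odds ratio, case count or power for the case-crossover, so there is no figure to reproduce.

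**Null odds ratio.** Let v_r and v_h be the probabilities of at least one contact in the referent and hazard windows, and p the probability that an NB order is recorded in a window with a contact. All three are assumed. Exposure probabilities are v_r·p and v_h·p. With no drug effect, the matched-pair odds ratio is

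OR = [v_h·p·(1 − v_r·p)] / [v_r·p·(1 − v_h·p)].

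Example with v_r = 0.60, v_h = 0.70, p = 0.5: (0.35 × 0.70) / (0.30 × 0.65) = 0.245 / 0.195 = 1.26.

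| v_r to v_h | p = 0.3 | p = 0.5 | p = 0.7 |
|---|---|---|---|
| 0.60 to 0.70 | 1.21 | 1.26 | 1.33 |
| 0.70 to 0.80 | 1.19 | 1.24 | 1.32 |
| 0.60 to 0.75 | 1.32 | 1.40 | 1.53 |

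**Allowing for dispensings.** A refill dispensing in claims needs no visit. Section 8.1 puts linked claims at about 64% of NB initiators at some point in time. As a best case, let that 64% keep the referent probability in both windows. Write b = v_h·p(1 − v_r·p), c = v_r·p(1 − v_h·p) and k = v_r·p(1 − v_r·p). Then

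OR = (0.36b + 0.64k) / (0.36c + 0.64k).

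In the example this is (0.0882 + 0.1344) / (0.0702 + 0.1344) = 0.2226 / 0.2046 = 1.09. Over the first two rows of the table the range is 1.07-1.11, and over the third it is 1.11-1.17.

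**If extra contacts yield fewer orders.** If contacts beyond the usual level produce NB orders at half the usual rate, replace v_h by v_r + (v_h − v_r)/2. The ranges become 1.09-1.15 and 1.16-1.24. If they produce none, the odds ratio is 1.00.

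**Downward case.** Let order opportunities change by a factor m, so that p_h = 1 − (1 − p_r)^m, where p_r and p_h are the exposure probabilities. With m = 0.75 and p_r from 0.05 to 0.60, the null odds ratio runs from 0.75 down to 0.66.

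**Chance of a misleading result.** Cases: 37,000 × 0.002 per year × 2 years = 148, using the plan's initiator count and MACE rate and an assumed two-year follow-up. A simulation with no drug effect let patients differ in their underlying order rate, made every record depend on visits, and applied an exact test to discordant pairs. The chance of a significant odds ratio above 1 was about 2% with no visit rise, 14% with a 1.25-fold rise and 41% with a 1.5-fold rise (odds ratios about 1.00, 1.32 and 1.65).

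**Precision of a lorcaserin comparison.** Lorcaserin cases: 16,000 × 0.002 × 2 = 64. In the 1.5-fold scenario about 36.5% of pairs are discordant, giving about 54 for NB and 23 for lorcaserin. At an odds ratio of 1.65 these split about 33.6/20.4 and 14.3/8.7. The variance of the log ratio of odds ratios is 1/33.6 + 1/20.4 + 1/14.3 + 1/8.7 = 0.264, so SE = 0.514. The 95% CI around a ratio of 1.0 is exp(±1.96 × 0.514), or about 0.37 to 2.7.

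**The case against.** The strongest reply is that the bias is possible, not shown. No part of the plan says that contacts rise before MACE. The contact rates, the order share and the premise that extra contacts yield orders at the usual rate are all assumed. Dispensings dilute the effect, and its direction is open. This stands: the size is a range under assumptions, and it can be small or reversed. The 64% dilution is itself optimistic, because section 6.2 names CONTRAVE® as an example of a medicine not covered by health plans, so claims may miss fills.

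A reader might infer that the case-crossover cannot serve its purpose at all. The documents do not support that. Section 10.2 says only that it will help inform, and limits its claim to factors that do not vary. Section 5 places it among other sensitivity analyses. It keeps its value against time-fixed confounders.

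A reader might also object that the case-crossover compares NB with no NB while the cohort compares NB with lorcaserin, so the two cannot be set side by side. If lorcaserin is cardiovascular-neutral, as section 5 holds, both contrasts target roughly the same effect. Section 9.5.2 also already plans current, recent and past-use categories. The difference in contrast is not a defect on the plan's own premises.

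Finally, dividing the NB odds ratio by a lorcaserin odds ratio might look like a complete correction. It removes only a trend shared by both drugs, needs similar persistence on both, and is too imprecise to separate 1.0 from 1.2-1.5.

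**Conclusion.** The point holds in a limited form. As specified, the case-crossover cannot distinguish a drug effect from a within-person change in care before MACE, and section 10.2 does not say so. With no drug effect the odds ratio would be about 1.2-1.5 under the assumed contact and order rates, about 1.07-1.17 if everyone with linked claims were unaffected, and below 1 if prescribing falls. Whether any such change occurs in these data is unknown until contacts are counted.

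The primary cohort estimate is untouched. This is a cheap improvement to a supporting analysis and to the wording around it.

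**What to change.** - **Section 9.5.3, contact adjustment.** Keep the planned conditional logistic model. Add a second with the number of outpatient contacts in each window as a covariate, and report both.
- **Sections 6.3 and 9.5.3, negative control.** Run the same case-crossover on lorcaserin cases as a supporting negative-control exposure. Report its odds ratio with a 95% CI, label it imprecise, and do not make it the headline comparison with the cohort IRR.
- **Section 10.2, interpretation.** State that the check addresses time-fixed confounding only. State in advance that an odds ratio that moves on contact adjustment, or a similar odds ratio for lorcaserin, points to care before the event rather than to a drug effect.

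The cost is a few sentences, one covariate and a re-run of existing code on data already held. There are two downsides. Adjusting for contacts may over-adjust if NB itself causes visits, which is why both models are reported. Lorcaserin cases will also be few, perhaps 64 with two years of follow-up.

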## 11 PROTECTION OF HUMAN SUBJECTS

Confidentiality of patient records will be maintained at all times. All analyses will be performed in accordance with applicable laws and regulations. All study reports will only contain aggregated results and will not identify individual patients or physicians. At no time during the study will Currax, Exponent, or any consultants on the study receive patient-identifying information.

## 12 MANAGEMENT AND REPORTING OF ADVERSE EVENTS

For this study using previously collected and deidentified electronic healthcare data, the research team does not anticipate any new adverse events to be identified. If, however, new adverse events are found during the course of the study, they will be vetted through the

pharmacovigilance processes at Currax Pharmaceuticals LLC and reported to regulatory authorities, as appropriate.

## **13 PLANS FOR DISSEMINATION AND COMMUNICATING STUDY RESULTS**

A report of the findings of this study will be presented to FDA upon finalization of study output. Additionally, Currax Pharmaceuticals LLC intends for the research team to publish the results in a peer reviewed journal expeditiously and in keeping with ISPE GPP (2015) and authorship guidelines presented by the International Committee of Medical Journal Editors (ICMJE) recommendations (2019).

